10.3. Statistical Analyses

10.3.1. General Statistical Considerations

Statistical analysis of this study will be the responsibility of Lilly or its designee.

Because the medical conditions being treated in this study are rare, it is anticipated that relatively few patients with each condition will be enrolled. Therefore, no formal statistical analyses are planned. Instead, descriptive summaries, where applicable, and data listings will be the main tools used to summarize the results from this study. Two-dimensional plots of various data may be utilized to explore the relationship between variables of interest. For example, plots of final dose level versus efficacy measures may be used to explore recommended dosing guidelines, and plots of efficacy measures versus laboratory measures may be used to explore risk/benefit relationships.

10.3.2. Treatment Group Comparability

10.3.2.1. Patient Disposition

A list of all enrolled patients and their reason for discontinuation from the study will be created.

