- r Baricitinib concentration samples will be collected, as described in Section 9.5. Additional unscheduled PK samples may be collected after Visit 6, as needed, for safety monitoring in patients with eGFR <60 mL/min/1.73 m².
- s Biomarkers may include IP-10/CXCL10 and IRG-S ([Appendix 2](#)). Samples for IRG-S will be collected in RNA PAXgene tube.
- t NNS/CANDLE only.
- u SAVI and AGS only.
- v Pharmacogenetic sample is collected at Visit 6. However, sample collection timing can be rescheduled to any other visit, if blood volume is limited at Visit 6.
- w An early termination visit is required if the patient discontinues from study treatment before Visit 36. All patients will move to ETV within 6 months after marketing authorization of baricitinib.
- x Patients who achieve either study completion or early discontinuation will have a posttreatment safety follow-up visit (V801) approximately 28 days after the last dose of IP. Patients who will transition from this study to commercial baricitinib are not required to have Visit 801. In this case, it will not be considered a protocol violation if the post treatment follow up period is not performed.
- y If a urine sample is unable to be collected in patients, particularly those who have not been toilet trained or those who have physical impairment caused by primary disease, this will not be considered to be a protocol violation provided that the site maintains appropriate documentation of why the sample is missing.

Note: Sites should make every attempt to schedule patient visits within the defined window. Exceptions to these windows may be granted under certain circumstances with prior approval of the Lilly clinical research physician or designee.

3. Introduction

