8.1. Discontinuation from Study Treatment

8.1.1. Permanent Discontinuation from Study Treatment

In rare instances, it may be necessary for a patient to permanently discontinue (definitive discontinuation) study intervention. When necessary, a participant may be permanently discontinued from study intervention. If so, the participant will remain in the study and follow procedures for remaining study visits, as shown in the Schedule of Activities (see Section 2).

Possible reasons leading to permanent discontinuation of investigational product:

Laboratory test results

Hepatic event or Liver test abnormality. A patient who is discontinued from investigational product due to a hepatic event or liver test abnormality should have additional hepatic safety data collected via eCRF.

Discontinuation of the investigational product for abnormal liver tests should be considered by the investigator when a patient meets one of the following conditions after consultation with Lilly or its designee:

- ALT or AST $>8 \times$ ULN
- ALT or AST $>5 \times$ ULN for more than 2 weeks after temporary interruption of investigational product
- ALT or AST $>3 \times$ ULN and total bilirubin (TBL) $>2 \times$ ULN or international normalized ratio (INR) >1.5
- ALT or AST $>3 \times$ ULN with the appearance of fatigue, nausea, vomiting, right upper-quadrant pain or tenderness, fever, rash, and/or eosinophilia ($>5\%$)
- Alkaline phosphatase (ALP) $>3 \times$ ULN that is deemed to be of liver origin and drug related
- ALP $>2.5 \times$ ULN and TBL $>2 \times$ ULN
- ALP $>2.5 \times$ ULN with the appearance of fatigue, nausea, vomiting, right quadrant pain or tenderness, fever, rash, and/or eosinophilia ($>5\%$)

Other Laboratory Abnormality Results

Discontinuation of the investigational product should be considered by the investigator when a patient meets one of the following conditions after consultation with Lilly or its designee:

- WBC count <1000 cells/ μ L
- ANC <500 cells/ μ L
- lymphocyte count <200 cells/ μ L
- hemoglobin <6.5 g/dL

Note: If any of the above specific abnormalities are considered a feature of the disease (NNS/CANDLE, SAVI, or AGS) and the investigator determines that it is in the best interest of the patient to continue treatment, patients may continue the investigational product. The reason for the decision will be documented in the medical record after discussion with Lilly or its designee.

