9.2. Adverse Events

Investigators are responsible for monitoring the safety of patients who have entered this study and for alerting Lilly or its designee to any event that seems unusual, even if this event may be considered an unanticipated benefit to the patient.

The investigator is responsible for the appropriate medical care of patients during the study.

Investigators must document their review of each laboratory safety report.

The investigator remains responsible for following, through an appropriate healthcare option: AEs that are serious or otherwise medically important; considered related to the investigational product or the study; or that caused the patient to discontinue the investigational product before completing the study. The patient should be followed until the event resolves, stabilizes with appropriate diagnostic evaluation, or is reasonably explained. The frequency of follow-up evaluations of the AE is left to the discretion of the investigator.

The investigator will record all relevant AE and SAE information in the eCRF. After the ICF and Assent Form (as applicable) are signed, study site personnel will record via electronic data entry the occurrence and nature of each patient's preexisting conditions, including clinically significant signs and symptoms of the disease under treatment in the study. In addition, site personnel will record any change in the condition(s) and any new conditions as AEs. The investigators should record their assessment of the potential relatedness of each AE to protocol procedure and/or investigational product, via electronic data entry.

The investigator will interpret and document whether or not an AE has a reasonable possibility of being related to study treatment, or a study procedure, taking into account the disease, concomitant treatment or pathologies. A "reasonable possibility" means that there is a cause and effect relationship between the investigational product, and/or study procedure and the AE.

Planned surgeries and nonsurgical interventions should not be reported as AEs unless the underlying medical condition has worsened during the course of the study.

If a patient's investigational product is discontinued as a result of an AE, study site personnel must report this to Lilly or its designee via eCRF, clarifying if possible, the circumstances leading to any dosage modifications, or discontinuations of treatment.

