## 6.4. Patient Disposition

For enrolled population, a by-patient listing of the patient disposition (discontinued or completed) including the visit that occurred will be created. The listing will include the following information; patient ID, disease diagnosis, visit, disposition category (complete or the primary reasons for study discontinuation).

Frequency counts and percentages of patients who complete or discontinue early from the study will be summarized separately by disease diagnosis along with their reason for study discontinuation.

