### 6.12.2.1. Adverse Events

An overview of AEs including deaths, SAEs, TEAEs, and patients discontinued from study due to an AE will be summarized for the treatment period. Treatment Period includes all of three period: Dose-adjustment period, Primary treatment period and Maintenance treatment period.

By patient listing of all AEs, AEs leading to study treatment discontinuation, AEs leading to temporary study drug interruption and COVID-19 related AEs will be provided.

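### The AE overview and disposition outputs count only discontinuation from the study, and the protocol conflicts on whether stopping baricitinib is leaving the study, so an AE-driven drug stop may or may not appear in the summary row

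*Protocol*

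**What the plan says.** Three planned outputs are framed by exit from the study.

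- Protocol Section 10.3.2.1: "A list of all enrolled patients and their reason for discontinuation from the study will be created".
- SAP Section 6.4: "Frequency counts and percentages of patients who complete or discontinue early from the study will be summarized separately by disease diagnosis", with the reason shown. The accompanying by-patient listing uses a "disposition category (complete or the primary reasons for study discontinuation".
- SAP Section 6.12.2.1, AE overview: "patients discontinued from study due to an AE will be summarized for the treatment period", alongside deaths, SAEs and TEAEs.

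One planned output looks at stopping the drug. It is a listing in the same SAP section: "By patient listing of all AEs, AEs leading to study treatment discontinuation, AEs leading to temporary study drug interruption".

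On what happens after a permanent stop of baricitinib, Protocol Section 8.1.1 states: "If so, the participant will remain in the study and follow procedures for remaining study visits". Section 5.1 sends patients who stop study treatment after at least one dose to the early termination visit (ETV), with Visit 801 about 28 days after the last dose. Footnote w to the Schedule of Activities requires the ETV for any treatment stop before Visit 36.

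On marketing authorization, Section 5.1 and footnote w both state: "All patients will move to ETV within 6 months after marketing authorization of baricitinib". Section 5.1 also makes commercial availability one of two planned ends of treatment. The other is Visit 36 (Week 244).

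**The concern.** The protocol treats stopping the drug and leaving the study as separate events. Sections 8.1 and 8.2 are separate, and Section 8.1.3 allows an inadvertently enrolled patient to continue with or without investigational product. The specific safety reasons (liver and blood-count limits, malignancy, venous thromboembolism, pregnancy, quantifiable HBV DNA, *Pneumocystis* pneumonia) stand in Section 8.1.1 as reasons to stop or consider stopping the product. Section 8.2 names none of them individually.

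A summary row that counts study exits is therefore an uncertain measure of how many patients stopped baricitinib because of harm. In a single-arm trial whose data support a regulatory submission (Protocol Section 10.3.6, SAP Section 6.15), that number and its reasons are a basic tolerability result. It should not depend on an unsettled definition. Reasons for drug stops not due to an AE, such as inadequate response or a family's decision, have no treatment-disposition output. The exposure listing in SAP Section 6.12.1 gives doses, dates and durations, with no stated item for the reason treatment ended. SAP Section 6.6 says compliance will not be calculated.

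**Working it through.** The documents give no figure to reproduce. The sample size of about 5 is a feasibility number, and no formal analysis is planned. The check is to follow one patient through the text and then show the scale.

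**Step 1. A patient permanently stops baricitinib for an AE before Visit 36.**

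- Under Section 8.1.1 the patient remains in the study. The disposition outputs then have no study discontinuation to record at the time of the stop, and the overview row need not count the patient.
- Under Section 5.1 and footnote w the patient goes to the ETV and then Visit 801. If that counts as leaving the study, the patient is counted with the AE as the reason.
- No passage says whether attending the ETV is itself discontinuation from the study.

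**Step 2. A patient leaves treatment because baricitinib is authorized.** The route is the ETV, which suggests early termination. Yet availability is also a planned end of treatment, which suggests completion. Neither document defines completion for this exit, so either coding is possible.

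**Step 3. Scale.** The scenario is an assumption, not document data: N = 5, one patient stops for an AE, and four leave on authorization before Visit 36.

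| Reading of a drug stop | Authorization exits coded as | Discontinued from study due to AE | Discontinued early from study |
|---|---|---|---|
| Stays in study (8.1.1) | complete | 0/5 | 0 + 0 = 0/5 |
| Stays in study (8.1.1) | early discontinuation | 0/5 | 0 + 4 = 4/5 |
| ETV taken as study exit (5.1, footnote w) | complete | 1/5 | 1 + 0 = 1/5 |
| ETV taken as study exit (5.1, footnote w) | early discontinuation | 1/5 | 1 + 4 = 5/5 |

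The number who permanently stopped baricitinib because of an AE is 1/5 = 20% in all four rows.

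The exact (Clopper-Pearson) 95% interval is 0 to 52.2% for 0/5 (upper limit 1 − 0.025^(1/5)) and 0.5 to 71.6% for 1/5 (lower limit 1 − 0.975^(1/5)). Neither count says much about an underlying rate. The issue is whether the trial's own facts are reported consistently.

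The SAP summarises by diagnosis, so one patient weighs more within a row: 1/3 = 33.3%, 1/2 = 50%, 1/1 = 100%.

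**The case against.** The strongest reply is that Section 8.1.1 refers to the Schedule of Activities for the remaining visits, and the Schedule itself requires the ETV. On that reading the passages agree. The patient leaves the schedule about a month after the last dose, and SAP Section 6.4 then needs a disposition. Showing zero would require coding a safety stop as complete, which nothing in the documents directs. Section 8.2 also has a general medical and safety ground and an investigator-decision ground, so safety exits do have a route into study discontinuation. This stands to the extent that a zero is not the inevitable result. It does not remove the ambiguity, because Section 8.1.1 says in terms that the patient remains in the study.

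A second reply is that the information is reported anyway. The SAP lists AEs leading to treatment discontinuation, and Protocol Section 9.2 requires reporting whenever a patient's "investigational product is discontinued as a result of an AE, study site personnel must report this to Lilly or its designee via eCRF". With about 5 patients, listings are a main reporting tool and a single case can be read directly. This also stands, and it limits the point to the summary rows and to reasons other than AEs.

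A reader might infer more: that stops for harm will be hidden while authorization exits are reported as early discontinuation. The documents do not support that. No passage says authorization exits are early discontinuations, and SAP Section 6.4 would show the reason for any exit coded that way. The inference also needs two opposite rules at once. Attending the ETV would have to mean staying in the study for the AE patient and leaving early for the authorization patients.

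**Conclusion.** The point holds in a limited form. The disposition outputs and the AE overview are defined by study exit only, and the protocol passages that decide whether a permanent drug stop is a study exit are not reconciled. The overview row for one AE-driven stop among 5 patients can read 0% or 20%, with a larger swing within a diagnosis. This rests on an assumed scenario with N = 5 and on the absence of any rule linking the ETV to study discontinuation. The planned AE listing keeps the case visible, so this is inconsistent summarising and not loss of data. The classification of authorization exits is a secondary gap: it is undefined, and it does not carry the finding. The change is worth making, because a count of permanent drug stops gives the same answer under every reading.

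**What to change.** 1. In SAP Section 6.12.2.1, add an overview row for patients who permanently discontinued baricitinib because of an AE. Keep discontinuation from the study because of an AE as a second row.
2. In SAP Section 6.4, summarise treatment disposition with reason, by diagnosis, alongside study disposition.
3. Reconcile Protocol Section 8.1.1 with Section 5.1 and footnote w, and state whether attending the ETV counts as discontinuation from the study. Which follow-up rule should apply is for the sponsor to settle.
4. As a clarification, define completion and state how exits due to marketing authorization or commercial availability are classified. A category of their own would avoid the choice.

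The cost is small: wording plus one row or table, with no new procedures. Drug stops for an AE are already reported on the eCRF, and the first and last dose dates are already used for exposure. The SAP revision history places approval of Version 5 before final database lock, which is the natural point for the change. The downside is that the reported number of stops for an AE may rise.

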10.3.2.2. Patient Characteristics

A summary and list of demographic information and baseline characteristics of all enrolled patients will be created.

10.3.2.3. Concomitant Therapy

Concomitant therapy will be recorded at each visit and will be classified according to the World Health Organization Drug Dictionary. Concomitant therapy will be reported in patient listings.

10.3.2.4. Treatment Compliance

Treatment compliance with investigational product will be summarized for each treatment period. Patients will be considered compliant for each study period if they miss <20% of the expected doses. Dose reductions or temporary withdrawal because of safety reasons will not be considered a protocol violation. Proportions of patients compliant will be reported in patient listing. Patient compliance will be further defined in the statistical analysis plan.

10.3.3. Efficacy Analyses

The primary data presentation will be a summary or by-patient listings of the following items:

- change from baseline in the appropriate diary score by indication,
- baseline, final steroid doses and changes over time for those patients receiving steroids.

No formal statistical test of any hypothesis will be conducted.

Additional data displays such as descriptive summaries where applicable and listings of efficacy measures over time will be provided.

10.3.4. Safety Analyses

Safety measures will be summarized and/or listed. Standard listings will include TEAEs, SAEs, and results from laboratory tests. By definition, TEAEs are AEs that begin or increase in severity after the patient receives the first dose of baricitinib. Summaries of the incidence and event counts of TEAEs and SAEs, of abnormal shifts in laboratory values, or of per-visit distributions of laboratory results will be created. Other data, including body weight and height data will be reported in patient listing. Weight, height, occipital frontal circumference measurement (children less than 3 years old), and body mass index data will be merged to the Japanese children standard growth data issued by the Japanese Association for Human Auxology to compare subjects' growth with the standard (Isojima et al. 2016).

10.3.5. Pharmacokinetic/Pharmacodynamic Analyses

Graphical/Visual analysis of the baricitinib concentration-time profile will be conducted to compare it with JAGA study result. Population PK approach (eg, PK parameters estimation using previously established population PK model) may be conducted to characterize PK in Japanese patients with NNS/CANDLE, SAVI, and AGS, if appropriate.

Pharmacokinetic/Pharmacodynamic analyses (eg, similarity with Study JAGA in relationship between baricitinib exposure [eg, area under the drug plasma versus time concentration from time zero to 24 hours at steady state (AUC_{0-24,ss})] and IFN-related biomarkers, including, but not limited to, serum IP-10/CXCL10 level and IFN response gene score) may be explored. Other analyses may also be conducted, if deemed appropriate.

10.3.6. Interim Analyses

A primary database lock is planned after the first 5 patients complete the Week 32 visit or the early termination visit. The analysis based on data from the primary database lock will be

conducted by Lilly or its designee for New Drug Application submission. No multiplicity adjustment will be implemented.

Other interim database lock may be performed, if needed (eg, regulatory agency requests to submit most recent safety data of the study).

The final database lock will occur after all patients complete the study, including posttreatment follow-up.

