Patients will remain on their treatments for NNS/CANDLE therapy (excluding JAK inhibitors) during pre-treatment period based on investigator's discretion (see Section [7.7.1](#)). Patient can skip Visit 5 and proceed to dose adjustment period (Visit 6) instead of Visit 5 if biologic agents are not administered during pre-treatment period or an appropriate washout duration of biologic agents defined exclusion criterion #27 has already passed at Visit 5 (see Section [6.2](#) Exclusion criteria [27], Section [7.7.1](#)). The patients who are required Visit 5 will proceed to Visit 6 after washout of biologic agents.

Patients will be confirmed the eligibility again using the most recent laboratory test results prior to Visit 6 (see exclusion criterion #22).

The data through pre-treatment period is used for baseline of pre-treatment period when results in primary/maintenance treatment period are compared to that of pre-treatment period.

Dose Adjustment Period

Patients who meet all eligibility criteria will enter an 8-week dose adjustment period. The initial dose prescribed at Visit 6 will be determined based on weight class and eGFR (see [Table JAJE.5](#)). After Visit 6, the dose adjustment period will evaluate the optimal baricitinib dosage to the patients with NNS/CANDLE, SAVI, or AGS based on clinical response. If the patient's weight changes during the study and requires a change in the dosing regimens as outlined in [Table JAJE.5](#), the dose may be adjusted to meet the dosing regimen based on current weight. Steroid weaning may begin for patients who are receiving systemic corticosteroids (Section [7.7.2](#)). The detailed instructions are described in Sections [5.1.1](#).

Primary Treatment Period

After completing dose adjustment at Visit 9, each patient will receive an optimized dosage of baricitinib that was determined throughout the dose adjustment period. Patients should maintain their optimized baricitinib dosage during the primary treatment period as much as possible.

Primary treatment period is set for each patient as following:

- NNS/CANDLE patients: 12 weeks [after Visit 9 (Week 8) to Visit 12 (Week 20)]
- SAVI or AGS patients: 24 weeks [after Visit 9 (Week 8) to Visit 15 (Week 32)]

Dose modification: If the patient's weight changes during the study and requires a change in the dosing regimens as outlined in [Table JAJE.5](#), the dose may be adjusted to meet the dosing regimen based on current weight.

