10.1. Sample Size Determination

Because the medical conditions being treated in the study are very rare in Japan, it is anticipated that relatively few patients will be enrolled. Approximately 5 patients will be enrolled. The Sponsor will try to enroll more than 1 patient per disease.

However, given the scarcity of patient population for each of these target diseases in Japan, it may be possible that the study is completed without enrolling any patients for a specific disease if no eligible patients could be found.

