### 3. Revision History

SAP Version 1 was approved prior to the first patient visit of the study.

SAP Version 2 was approved prior to the database lock of primary treatment period. The overall changes and rationale for the changes incorporated in Version 2 were as follows:

Section	Revisions
6.1	To add the conversion factors of calculating Prednisone (or Equivalent) Dose
6.1.1	To remove the definition of baseline and endpoint in the pre-treatment period for CANDLE/NNS because there are no intervention in pre-treatment period.
6.4	To add summary of treatment disposition and detailed specifications of disposition listing.
6.5	To add the listing of medical history and pre-existing conditions.
6.6	To add the logic of calculating treatment compliance.
6.7	To add summary of concomitant medications.
6.8.3.1	To specify the endpoints of efficacy analyses for comparison with pre-treatment period.
6.12.2.1	To add the listing of COVID-19 related AEs .
6.14	To move the definition of protocol deviation for treatment non-compliance from section 6.6 and describe the Trial Issue Management Plan for assessing protocol deviations.

SAP Version 3 was approved prior to the 52 week database lock. The overall changes and rationale for the changes incorporated in Version 3 are as follows:

Section	Revisions
5	To update Figure JAJE.1 using the latest version of study design figure in the protocol.
6.6	To remove the method of calculation of treatment compliance.
6.8.3	To add interferon (IFN) signature score for the analysis of biomarkers.
6.8.3	To create spaghetti plot for efficacy parameters.
6.12.2.1	To add by-patient-listing of all AEs, AEs leading to study discontinuation, AEs leading to temporary study drug interruption.
6.12.4	To add the listing of BK virus tests.
6.15	To add the interim analysis to assess efficacy and safety of baricitinib with 1 year exposure.

SAP Version 4 was approved after 52 week database lock. The change was to translate a Japanese manuscript in the Section 7 (References) into English.

SAP Version 5 will be approved before final database lock. The change is made to modify Figure JAJE.1 to be consistent with the I4V-JE-JAJE(e) Clinical Protocol.

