#### **NNS/CANDLE, SAVI, AGS**

**Baseline of the baricitinib treatment period** which includes dose adjustment period, primary treatment period and maintenance treatment period will be defined as the last available value before the first dose of baricitinib. In most cases, this will be the measure recorded at Week 0 (Visit 6). Change from baseline will be calculated as the visit value of interest minus the baseline value.

**Endpoint of the baricitinib treatment period** will be the last non-missing postbaseline measurement during the baricitinib treatment period. Major interest is the endpoint of the primary treatment period. Any measurements collected after the first dose of baricitinib will be considered a postbaseline measurement.

**Baseline of the post follow-up period** is defined as the date of the final visit or early termination in the treatment period. **Endpoint of the post follow-up period** is Visit 801.

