## 6.2. Handling of Dropouts or Missing Data

If the year of birth is collected but the day and month are missing then July 1st will be used as the imputed month and day for purposes of age calculation.

For continuous measure, observed case analyses will be performed. In addition, a last observation carried forward (LOCF) imputation replaces missing data with the most recent non-missing post-baseline assessment for the endpoint of primary treatment period and maintenance treatment period.

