## 6.3. Use of an “Efficacy Subset” of Patients

**Entered population** set includes those patients who sign the informed consent form directly or through their legally acceptable representatives.

**Enrolled population** set includes all patients who have entered the study and who are not considered screen fails at or before Visit 6 (i.e. patients not excluded due to not meeting inclusion criteria or meeting exclusion criteria during screening/pre-treatment period).

**Efficacy population** set includes all enrolled patients who have at least one dose of baricitinib.

**Safety population** set includes all enrolled patients who receive at least 1 dose of baricitinib and who did not discontinue the study for the reason “Lost to Follow-up” at the first postbaseline visit (Visit 7).

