## 6.15. Interim Analyses and Data Monitoring

An interim analysis is planned after all planned enrolled patients completed the primary treatment period or early discontinued at or prior to the primary treatment period. The purpose of the interim analysis is to support regulatory submission of the Study JAJE data.

Another interim analysis is also planned after all planned enrolled patients completed Week 52 (Visit 20) or early discontinued at or prior to Visit 20 in order to evaluate the efficacy and safety of baricitinib with 1 year exposure.

Adjustment to type I error is not applicable as Study JAJE is a single arm, open-label program.

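### Do Protocol 10.3.6 and SAP 6.15 set conflicting cuts for the submission analysis, and could LOCF then fill in visits that are not yet due?

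*Protocol*

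**What the plan says.** Protocol 10.3.6 describes the lock that feeds the New Drug Application: "A primary database lock is planned after the first 5 patients complete the Week 32 visit or the early termination visit". It draws no distinction by disease. It also allows other interim locks and provides for a final lock once all patients have finished.

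SAP 6.15 describes the analysis that supports regulatory submission: "An interim analysis is planned after all planned enrolled patients completed the primary treatment period or early discontinued". The length of the primary treatment period comes from Protocol 5.1. One entry begins "NNS/CANDLE patients: 12 weeks [after Visit 9 (Week 8) to Visit 12 (Week 20"; the entry for SAVI and AGS runs 24 weeks, to Visit 15 (Week 32). A second SAP interim analysis, at Week 52, is separate.

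On numbers, Protocol 10.1 says: "Approximately 5 patients will be enrolled. The Sponsor will try to enroll more than 1 patient per disease". SAP 5.2 gives the same figure.

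On missing values, SAP 6.2 plans observed-case analyses and adds LOCF, which "replaces missing data with the most recent non-missing post-baseline assessment for the endpoint of primary treatment period and maintenance treatment period". SAP 6.1.1 adds: "Any measurements collected after the first dose of baricitinib will be considered a postbaseline measurement". The efficacy population in SAP 6.3 "set includes all enrolled patients who have at least one dose of baricitinib".

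On timing, the SAP revision history records: "SAP Version 2 was approved prior to the database lock of primary treatment period". Version 4 followed the 52-week lock.

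**The concern.** Two documents describe one regulatory analysis and give it different triggers. They differ in time point (Week 32 for everyone, or Week 20 for NNS/CANDLE) and in the patients counted (the first 5, or all planned enrolled). Neither document defines those two phrases or says what happens to a patient beyond the fifth.

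The LOCF rule makes this look worse. It sets no condition that the patient has dropped out or that the visit has fallen due. If more than five patients enrolled and the database were locked on the protocol rule, a recently dosed patient would be in the efficacy population without a Week 20 or Week 32 value. Read literally, SAP 6.2 would put that patient's latest value in its place, possibly one from the dose-adjustment period. Groups are very small: with two patients in a disease (an assumption), one carried value is 1/2 = 50% of the mean; with three it is 1/3, about 33%. At stake would be a misleading LOCF summary in the submission, and a reader unable to tell which cut had been used.

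**Working it through.** The plan has no power or error-rate figure to reproduce: the sample size rests on feasibility and the analysis is descriptive. The check is calendar arithmetic and a reading of the two rules together.

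**Inputs.** Week 20 is Day 141 and Week 32 is Day 225 (Protocol Table JAJE.2). Primary time points are Week 20 for NNS/CANDLE and Week 32 for SAVI and AGS (SAP Table JAJE.1, footnote a). Early visits fall at Weeks 2, 4, 8 and 12. Accrual dates are not given, so start weeks below are assumptions. No early termination is assumed; both rules treat it as meeting the condition.

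**1. Size of the difference for one NNS/CANDLE patient.** 225 − 141 = 84 days = 12 weeks.

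**2. Earliest permitted cut with five patients.** Let patient i start at calendar week s(i).

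- Protocol: P = max of s(i) + 32.
- SAP: S = max of s(i) + 20 for NNS/CANDLE and s(i) + 32 for SAVI/AGS.

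Since 32 ≥ 20, P is never before S, so meeting the protocol rule also meets the SAP rule. If the last NNS/CANDLE patient starts g weeks after the last SAVI/AGS patient (g > 0), then P = 32 + g, S = max(32, 20 + g), and P − S = min(g, 12).

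| Five patients | P (week) | S (week) | P − S |
|---|---|---|---|
| 5 NNS/CANDLE, same start | 32 | 20 | 12 |
| 5 SAVI/AGS, same start | 32 | 32 | 0 |
| 3 NNS/CANDLE + 2 SAVI/AGS, same start | 32 | 32 | 0 |
| 4 SAVI/AGS at 0, last NNS/CANDLE at 6 | 38 | 32 | 6 |
| 4 SAVI/AGS at 0, last NNS/CANDLE at 12 | 44 | 32 | 12 |
| 4 SAVI/AGS at 0, last NNS/CANDLE at 24 | 56 | 44 | 12 |

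At S every patient still on treatment has reached the primary time point for the disease, and P is no earlier. The Week 20 and Week 32 values are therefore already due under either rule. The later cut only adds maintenance-period visits for NNS/CANDLE.

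**3. A sixth patient (assumed), first dosed d weeks after the fifth.** At the protocol lock this patient is at week 32 − d.

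- Short of Week 32 (SAVI/AGS): any d > 0.
- Short of Week 20 (NNS/CANDLE): d > 12.
- Before Visit 10 (Week 12), so with dose-adjustment values only: d > 20. With at least the Week 2 visit done: d ≤ 30.
- A Week 8 value would be carried 20 − 8 = 12 weeks (NNS/CANDLE) or 32 − 8 = 24 weeks (SAVI/AGS).

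The same patterns under both rules, with five SAVI/AGS patients starting at week 0:

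| Sixth patient | P | S | Sixth patient's week at P | Sixth patient at S |
|---|---|---|---|---|
| SAVI/AGS at 12 | 32 | 44 | 20 | Week 32 reached |
| NNS/CANDLE at 12 | 32 | 32 | 20 | Week 20 reached |
| NNS/CANDLE at 20 | 32 | 40 | 12 | Week 20 reached |
| SAVI/AGS at 20 | 32 | 52 | 12 | Week 32 reached |

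Both documents place the cut after a condition is met and neither sets a deadline. A lock at the later of P and S complies with both, and at that point no patient on treatment is short of the primary visit. This takes planned enrolled to cover everyone dosed.

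**4. Fewer than five patients.** Read literally, the protocol condition would never be met, while the SAP condition would be. A team would take the five as everyone enrolled.

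**The case for a change.** The strongest case for acting is that the mismatch stands in current text, the wording would cost little to align, and the sponsor has aligned the two documents before: an earlier protocol amendment changed the compliance section to match the SAP, and SAP Version 5 changes a figure to match the protocol. The LOCF gap is also real as text. It reaches the maintenance-period endpoint under either trigger, because treatment can run to Week 244 and continuing patients are still on treatment at the primary and Week 52 cuts.

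What stands is that the two sentences differ and that SAP 6.2 does not say a visit must be due. What does not stand is that the rules are incompatible, since one lock can meet both. SAP 6.2 is headed as dealing with dropouts or missing data, and a visit that has not fallen due is not missing in the ordinary sense. For the maintenance endpoint, SAP 6.1.1 already defines the treatment-period endpoint as the last available value. At an interim cut that is simply the latest status, shown beside by-visit results and listings, and the final lock replaces it.

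An obvious remedy can also do harm. Limiting LOCF to patients who discontinued or missed a visit, while showing all ongoing patients as observed only, gives opposite answers for an ongoing patient who missed Week 20 or Week 32. Nearly everyone may be ongoing at that cut, so it could switch LOCF off almost entirely.

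**Conclusion.** No change to the plan is needed. The documents give slightly different earliest dates for one descriptive analysis. With the planned five patients the dates differ by 0 to 12 weeks, and primary time-point data are due for every patient still on treatment under both rules. A distorted LOCF summary requires all of the following: a sixth patient, a start late enough to be short of the primary visit, a lock on the protocol rule before the SAP condition is met, and a reading of missing that covers future visits. The dose-adjustment version further requires a start more than 20 and up to 30 weeks after the fifth patient.

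Even in that case the observed-case result stands beside the LOCF result, patient listings show each visit, no hypothesis is tested, and the Week 52 and final analyses give later looks. The SAP revision history implies that the submission lock is already past, so new trigger wording would alter nothing already produced. The study report is the natural place to state the cut date used, and SAP 6.1 already sends lesser departures from the protocol's analysis methods there.

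The conclusion assumes that planned enrolled means everyone dosed, and that analysts do not impute a visit before it falls due. Both are the ordinary readings.
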